### **3.3.5 Replacement of subjects**

In case some subjects do not complete the trial as per protocol, the Trial Clinical Monitor together with the Trial Pharmacokineticist and the Trial Statistician are to decide if and how many subjects will be replaced. A maximum of 5 subjects will be replaced. Thus, the total number of subjects entered and dosed in this trial will not exceed 50. A replacement subject

Proprietary confidential information © 2019 Boehringer Ingelheim International GmbH or one or more of its affiliated companies

will be assigned a unique study subject number, and will be assigned to the same treatment sequence as the subject he or she replaces.

## **4. TREATMENTS**

### **4.1 TREATMENTS TO BE ADMINISTERED**

BI 409306 and matching placebos will be manufactured by BI Pharma GmbH & Co. KG.

Moxifloxacin (Avalox®) 400 mg tablets produced by Bayer Vital, Leverkusen, Germany, will be sourced from a local pharmacy.

#### **4.1.1 Identity of BI investigational products**

The characteristics of the test product are given below:

Substance: BI 409306  
Pharmaceutical formulation: Film-coated tablet  
Source: BI Pharma GmbH & Co. KG, Germany  
Unit strength: 50 mg  
Posology: 1-0-0 on Day 1 of treatment 1 [L],  
5-0-0 on Day 1 of treatment 2 [H]  
Route of administration: p.o.  
Duration of use: Single dose in treatments 1 [L] and 2 [H]

The characteristics of the reference products are given below:

Name: Avalox®  
Substance: Moxifloxacin  
Pharmaceutical formulation: Film-coated tablet  
Source: Bayer Vital, Leverkusen, Germany  
Unit strength: 400 mg  
Posology: 1-0-0 on Day 1 of treatment 3 [M]  
Route of administration: p.o.  
Duration of use: Single dose in treatment 3 [M]

Substance: Placebo matching to BI 409306 50 mg tablet  
Pharmaceutical formulation: Film-coated tablet  
Source: BI Pharma GmbH & Co. KG, Germany  
Unit strength: n.a.  
Posology: 4-0-0 on Day 1 of treatment 1 [L],  
5-0-0 on Day 1 of treatment 4 ([P1] and [P2])  
Route of administration: p.o.  
Duration of use: Single dose in treatments 1 [L] and 4 ([P1] and [P2])

#### 4.1.2 Method of assigning subjects to treatment groups

According to the calculated sample size, 5 cohorts are planned. Prior to start of the study, subjects willing to participate will be recruited to cohorts according to their temporal availability. Since the study includes healthy volunteers from a homogenous population, relevant imbalances between the treatment sequences are not expected.

The list of study subject and medication numbers will be provided to the trial site in advance. The allocation of subjects to study subject numbers will be performed prior to the first administration of trial medication. For this purpose, the subjects will be allocated to a study subject number by drawing lots. Once a subject number has been assigned, it cannot be reassigned to any other subject.

The randomisation procedure is described in Section [7.5](#).

The overall number of 45 subjects is planned to be split into 5 cohorts. In case subjects need to be replaced an additional cohort may be added or replacement subjects may be added to existing cohorts allowing up to 12 subjects on treatment days. The planned cohort size allows a timely conduct of the study with reasonable duration minimizing seasonal impact on trial data while at the same time still allows adequate medical surveillance of the subjects. Within one cohort, subjects will be treated on the same calendar day. No minimal time interval between dosing is defined. This is acceptable from a safety point of view (for safety margin margins refer to Section [1.2.2.4](#); for discussion of study-associated risk and safety measures see Section [2.3](#)).

#### 4.1.3 Selection of doses in the trial

The dose of 50 mg was selected in order to measure the effect of the anticipated therapeutic dose of BI 409306. The dose of 250 mg was selected in order to measure the effect of a tolerable supra-therapeutic dose of BI 409306 on cardiac safety (see Section [1.2](#)).

#### 4.1.4 Drug assignment and administration of doses for each subject

This trial is a five-period crossover study. All subjects will receive the 4 treatments (two placebo periods) in randomised order. The treatments to be evaluated are outlined in Table [4.1.4: 1](#) below.

Table 4.1.4: 1

Dosage and treatment schedule, oral administration

Treatment	Substance	Formulation	Unit strength	Number of units	Total dose
1 [L]	BI 409306	Tablet	50 mg	1	50 mg
	Placebo to BI 409306 50 mg	Tablet	---	4	
2 [H]	BI 409306	Tablet	50 mg	5	250 mg
3 [M]	Moxifloxacin	Tablet	400 mg	1	400 mg
4 ([P1] and [P2])	Placebo to BI 409306 50 mg	Tablet	---	5	---

The medication will be administered as a single oral dose together with about 240 mL of water to a subject in a standing position under supervision of the investigating physician or an authorised designee. The so-called four-eye principle (two-person rule) should be applied for administration of trial medication if correct dosage cannot be ensured otherwise.

Administration will be performed following an overnight fast which is to start no later than 10 h before scheduled dosing.

Subjects will be kept under close medical surveillance until at least 24 h following BI 406309, moxifloxacin and placebo administration. Holter ECG will be recorded from up to 3 hours prior to drug administration until at least 24 hours after drug administration. During the first 2 h after drug administration, subjects are not allowed to lie down (i.e. no declination of the upper body of more than 45 degrees from upright posture) except for medical examinations, single ECG recordings and triplicate ECG extraction time points and preceding resting time. For restrictions with regard to diet see Section [4.2.2.2](#).

The treatments will be separated by a wash-out phase of at least 6 days.

#### **4.1.5 Blinding and procedures for unblinding**

The two doses of BI 409306 and matching placebos will be administered double-blind with regard to the subjects and the investigators (as well as the research staff at the trial site) in order to eliminate observer or performance bias; moxifloxacin will be administered open-label. This means avoiding systematic differences in assessments regarding the subject's treatment (active or placebo). Persons directly involved in the clinical conduct or statistical analysis of the trial will not have access to the treatment allocation prior to database lock.

At the sponsor, access to the randomisation schedule is restricted to the Clinical Trial Support group, who generates the randomisation code and labels, to the Pharmaceutics Department, where the packaging takes place, to the independent programmer as described below, and to the trial bioanalyst.

Prior to trial initiation, the randomisation codes will be provided to an independent programmer, who will generate a list indicating the moxifloxacin treatment period for each subject in the form of e.g. X-X-M-X-X or M-X-X-X-X. This list will be provided to the

Proprietary confidential information © 2019 Boehringer Ingelheim International GmbH or one or more of its affiliated companies

clinical site to enable study set up. The independent programmer will confirm that the original randomisation codes will be treated confidentially.

Prior to unblinding of the trial database, the randomisation codes will be provided to bioanalytical staff to allow them to exclude from the bioanalytical analyses PK samples taken from placebo-treated subjects. Bioanalytics will not disclose the randomisation code or the results of their measurements until the trial is officially unblinded.

The trial will only be unblinded after locking of the database.

Within the central ECG lab, the staff involved with interval measurements and morphological analyses will be blinded with respect to the treatment and also with regard to the recording date and time as well as planned time points of the ECGs. The interval measurements for a given subject will be performed in a random and blinded sequence by a single technician.

#### **4.1.5.1 Procedures for emergency unblinding**

For this blinded trial, the investigator will be supplied with a set of sealed envelopes containing the medication codes for each subject according to the randomisation scheme. The envelopes will be kept unopened at the trial site until the end of data collection. An envelope may only be opened in emergency situations when the identity of the trial drug must be known to the investigator in order to provide appropriate medical treatment or to assure safety of trial participants. If the envelope for a subject is opened, the sponsor must be informed immediately. The reason for opening the code break must be documented on the envelope or appropriate CRF page along with the date and the initials of the person who broke the code. At the close-out visit all envelopes are collected.

#### **4.1.6 Packaging, labelling, and re-supply**

BI 406309 and matching placebos will be provided by the Department of Pharmaceutical Development of Boehringer Ingelheim Pharma GmbH & Co. KG, Biberach, Germany.

The clinical trial supply consists of containers holding the trial medication which are labelled with trial identification. The required information according to the German Drug Law as well as Annex 13/EU GMP Guideline will be provided on the containers. Each container will contain 2 blisters with 7 tablets each of either BI 409306 50 mg or matching placebo. The containers will be labelled with:

- BI trial number
- Name of product and strengths or identification code
- Pharmaceutical dosage form, quantity of dosage units
- Route and mode of administration
- Term 'For Clinical Trial Use' (domestic language)
- Sponsor name and address
- Storage conditions
- Use-by date
- Subject or medication number
- Visit number
- Batch number

Proprietary confidential information © 2019 Boehringer Ingelheim International GmbH or one or more of its affiliated companies

At the trial site, drug will be dispensed by the investigator or authorised designee according to medication and visit numbers (table 4.1.6: 1):

**Table 4.1.6: 1** Content of the blisters containing trial medication for treatments 1 [L], 2 [H], and 4 ([P1] and [P2])

Treatment	Blister	Number of units (tablets) to be dispensed #	Blister containing *	Unit strength	Total dose
1 [L]	Blister 1	1	BI 409306 50 mg tablet	50 mg	50 mg
	Blister 2	4	Matching placebo tablet	---	
2 [H]	Blister 1	1	BI 409306 50 mg tablet	50 mg	250 mg
	Blister 2	4	BI 409306 50 mg tablet	4x 50 mg	
4 ([P1] and [P2])	Blister 1	1	Matching placebo tablet	---	---
	Blister 2	4	Matching placebo tablet	---	---

\* The information about blister content will not be provided to the clinical site

# Each blister contains 7 tablets; only 1 tablet (of blister 1) and 4 tablets (of blister 2) will be used

The telephone number of the sponsor and name, address and telephone number of the trial site are given in the subject information form. The EudraCT number is indicated on the title page of this protocol as well as on the subject information and informed consent forms. Examples of the labels will be available in the ISF.

Moxifloxacin (Avalox®) will be sourced from a local pharmacy. It will not be labelled. The original packaging (German commodity) will be used for the open-label part of the trial.

No re-supply is planned.

#### **4.1.7 Storage conditions**

Drug supplies will be kept in their original packaging and in a secure limited access storage area according to the recommended (labelled) storage conditions. Where necessary, a temperature log must be maintained to ensure that the drug supplies are stored at the correct temperature. If the storage conditions are found to be outside the specified range, the local clinical monitor (as provided in the list of contacts) is to be immediately contacted.

#### **4.1.8 Drug accountability**

The investigator will receive the investigational drugs delivered by the sponsor when the following requirements are fulfilled:

- Approval of the trial protocol by the IRB / ethics committee
- Approval/notification of the regulatory authority, e.g. competent authority
- Availability of the curriculum vitae of the principal investigator
- Availability of a signed and dated clinical trial protocol

Proprietary confidential information © 2019 Boehringer Ingelheim International GmbH or one or more of its affiliated companies

Only authorised personnel as documented in the form 'Trial Staff List' may dispense medication to trial subjects. The trial medication must be administered in the manner specified in the CTP. All unused medication will be disposed locally by the trial site upon written authorisation by the clinical monitor. Receipt, usage and disposal must be documented on the respective forms. Account must be given for any discrepancies.

The investigator must maintain records of the product's delivery to the trial site, the inventory at the site, the use by each subject, and the disposal of unused products.

These records will include dates, quantities, batch / serial numbers, expiry ('use-by') dates, and the unique code numbers assigned to the investigational products and trial subjects. The investigator will maintain records that document adequately that the subjects were provided the amounts of tablets specified by the CTP, and that reconcile all investigational products received from the sponsor. At the time of disposal, the investigator must verify that no remaining supplies are in the investigator's possession.

## **4.2 OTHER TREATMENTS, EMERGENCY PROCEDURES, RESTRICTIONS**

### **4.2.1 Other treatments and emergency procedures**

There are no special emergency procedures to be followed. No additional treatment is planned. However, in case of adverse events in need of treatment, the investigator can authorise symptomatic therapy. In those cases, subjects will be treated as necessary and, if required, kept under supervision at the trial site or transferred to a hospital until all medical evaluation results have returned to an acceptable level.

### **4.2.2 Restrictions**

#### **4.2.2.1 Restrictions regarding concomitant treatment**

In principle, no concomitant therapy is allowed. All concomitant or rescue therapies will be recorded (including time of intake on study days) on the appropriate pages of the CRF.

Ibuprofen may be used as an analgesic drug if needed.

Proprietary confidential information © 2019 Boehringer Ingelheim International GmbH or one or more of its affiliated companies

#### 4.2.2.2 Restrictions on diet and life style

While admitted to the trial site the subjects are restricted from consuming any other foods or drinks than those provided by the staff. Standardised meals will be served at the time points described in the [Flow Chart](#). No food is allowed for at least 4 h after drug intake.

From 1 h before drug intake until lunch, fluid intake is restricted to the water administered with the drug, and an additional 240 mL of water at 2 h and 4 h post-dose (mandatory for all subjects). From lunch until 24 h post-dose, total fluid intake is restricted to 3000 mL. For fasting requirements see Section [4.1.4](#).

Grapefruits, Seville oranges (sour or bitter oranges) and their juices, and dietary supplements and products including St. John's wort (*Hypericum perforatum*) are not permitted starting 7 days before the first administration of trial medication until after the last PK sample in the study is collected.

Smoking is not allowed starting from 30 days prior to screening until end-of-trial examination.

Alcoholic beverages are not allowed from 48 h before administration of trial medication until the end of hospitalisation period in each treatment period.

Methylxanthine-containing drinks or foods (such as coffee, tea, cola, energy drinks, and chocolate) are not allowed during in-house confinement.

Excessive physical activity (such as competitive sport) should be avoided starting 7 days before the first administration of trial medication until the end of trial examination.

Direct exposure to the sun (that is, sunbathing) or exposure to solarium radiation should be avoided during the entire study.

If female subjects of child-bearing potential are included, adequate contraception is to be maintained throughout the course of the trial (see Section [3.3.2](#) for adequate measures).

### 4.3 TREATMENT COMPLIANCE

Compliance will be assured by administration of all trial medication in the study centre under supervision of the investigating physician or a designee. The measured plasma concentrations will provide additional confirmation of compliance.

Subjects who are non-compliant (for instance, who do not appear for scheduled visits or violate trial restrictions) may be removed from the trial and the CRF will be completed accordingly (for further procedures, please see Section [3.3.4.1](#)).

## 5. VARIABLES AND THEIR ASSESSMENT

### 5.1 EFFICACY - CLINICAL PHARMACOLOGY

#### 5.1.1 Endpoints of efficacy

No efficacy endpoints will be evaluated in this trial.

#### 5.1.2 Assessment of efficacy

Not applicable.

## 5.2 SAFETY

#### 5.2.1 Endpoints of safety

##### 5.2.1.1 Primary safety endpoints

The primary endpoint will be the maximum mean difference between each single dose of either 50 mg or 250 mg BI 409306 and placebo in QTcF changes from baseline between 20 min to 24 hours after drug administration. QTcF is the heart rate corrected QT interval according to Fridericia (see Section [7.3.2.5](#)).

##### 5.2.1.2 Secondary safety endpoints

- The maximum mean difference between moxifloxacin and placebo in QTcF changes from baseline between 20 min to 24 hours after drug administration.
- The maximum mean difference between each single dose of either 50 mg or 250 mg BI 409306 and placebo in HR changes from baseline between 20 min to 24 hours after drug administration. HR will be derived from the RR interval (see Section [7.3](#)).
- The minimum mean difference between each single dose of either 50 mg or 250 mg BI 409306 and placebo in HR changes from baseline between 20 min to 24 hours after drug administration.

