Reference product 1: Moxifloxacin (Avalox ® ) film-coated tablets (treatment 3)					
Dose: 400 mg					
Mode of admin.: Oral with 240 mL of water after an overnight fast of at least 10 h					
Reference product 2: Placebo matching to BI 409306 50 mg tablets (treatment 4)					
Dose: Not applicable					
Mode of admin.: Oral with 240 mL of water after an overnight fast of at least 10 h					
Duration of treatment: One day (single dose) for each treatment					
Criteria for pharmacokinetics:					
Criteria for safety:					
Primary endpoints: The maximum mean difference between BI 409306 and placebo in the QTcF changes from baseline between 20 min to 24 hours after drug administration, for each dose of BI 409306.					
Secondary endpoints: 

• The maximum mean difference between moxifloxacin and placebo in the QTcF changes from baseline for the time points 2, 3, and 4 hours after dosing (for assessment of assay sensitivity).

• The maximum mean difference between BI 409306 and placebo in heart rate (HR) changes from baseline between 20 min to 24 hours after drug administration, for each dose of BI 409306.

• The minimum mean difference between BI 409306 and placebo in HR changes from baseline between 20 min to 24 hours after drug administration, for each dose of BI 409306.

					

Proprietary confidential information © 2019 Boehringer Ingelheim International GmbH or one or more of its affiliated companies

Name of company: Boehringer Ingelheim		Tabulated Trial Protocol		
Name of finished product: Not applicable				
Name of active ingredient: BI 409306				
Protocol date: 08 February 2019	Trial number: 1289-0038		Revision date: 23 April 2019	

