### **7.1.2      Endpoints**

The primary endpoint will be derived based on the changes from baseline in QTcF at each time point between 20 min to 24 hours after drug administration of BI 409306 and placebo. For each of the 2 doses of BI 409306, the relevant outcome is the maximum mean difference between BI 409306 and placebo in the QTcF changes from baseline (see also Section [5.2.1.1](#)).

The secondary endpoints are based on (see also Section [5.2.1.2](#)):

- The QTcF changes from baseline at each time point between 20 min to 24 hours after drug administration of moxifloxacin and placebo (for assessment of assay sensitivity). The relevant outcome is the maximum mean difference between moxifloxacin and placebo in the QTcF changes from baseline for the time points 2, 3, and 4 hours after dosing.
- The changes from baseline in HR at each time point between 20 min to 24 hours after drug administration of BI 409306 and placebo. For each dose of BI 409306, the relevant outcomes are the maximum and the minimum mean differences between BI 409306 and placebo in HR changes from baseline after dosing. HR will be derived from the RR interval (see Section [7.3](#)).

Proprietary confidential information © 2019 Boehringer Ingelheim International GmbH or one or more of its affiliated companies

Safety and tolerability will be determined on the basis of further safety endpoints specified in Section [5.2.1.3](#).

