## 7.2 NULL AND ALTERNATIVE HYPOTHESES

The primary objective of this study will be assessed by testing for each dose of BI 409306 the null hypothesis that the mean difference in the QTcF changes from baseline between BI 409306 and placebo is greater than or equal to 10 msec at least for one time point after dosing, against the alternative hypothesis that the mean difference is below the threshold of 10 msec for all time points.

The conclusion that this tQT trial is negative as per ICH E14 (see Section [7.1.1](#)) will be based on the rejection of this null hypothesis for each of the two doses of BI 409306. This testing procedure is considered to be confirmatory, as the power calculations are based on this endpoint and the non-inferiority margin of 10 msec (see Section [7.6](#)). The one-sided tests will be performed at the 5% level, which is equivalent to the estimation of two-sided 90% confidence intervals because of the symmetry of the normal distribution.

For the assessment of assay sensitivity of the trial, the null hypothesis that the mean difference in the QTcF changes from baseline between moxifloxacin and placebo is less than or equal to 5 msec for all of the time points 2, 3, and 4 hours after dosing will be tested at the 5 % level, against the alternative hypothesis that the mean difference is above the threshold of 5 msec for at least one of the three time points. The Hochberg correction will be used for adjusting for multiplicity (see Section [7.3.2.1](#)).

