4. CHANGES IN THE PLANNED ANALYSIS OF THE STUDY

All analyses described in this TSAP are in accordance with the statistical methods described in the CTP.

Proprietary confidential information © 2019 Boehringer Ingelheim International GmbH or one or more of its affiliated companies

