5.2.2 Secondary endpoints

CTP Section 5.2.1.2:

- The QTcF changes from baseline at each time point between 20 min to 24 hours after drug administration of moxifloxacin and placebo (for assessment of assay sensitivity). The relevant outcome is the maximum mean difference between moxifloxacin and placebo in the QTcF changes from baseline for the time points 2, 3, and 4 hours after dosing.
- The changes from baseline in HR at each time point between 20 min to 24 hours after drug administration of BI 409306 and placebo. For each dose of BI 409306, the relevant outcomes are the maximum and the minimum mean differences between BI 409306 and placebo in HR changes from baseline after dosing. HR will be derived from the RR interval (see Section 9.1).

TSAP for BI Trial No: 1289-0038 Page 10 of 44

Proprietary confidential information © 2019 Boehringer Ingelheim International GmbH or one or more of its affiliated companies

TSAP for BI Trial No: 1289-0038 Page 11 of 44

Proprietary confidential information © 2019 Boehringer Ingelheim International GmbH or one or more of its affiliated companies

TSAP for BI Trial No: 1289-0038 Page 13 of 44

Proprietary confidential information © 2019 Boehringer Ingelheim International GmbH or one or more of its affiliated companies

Proprietary confidential information © 2019 Boehringer Ingelheim International GmbH or one or more of its affiliated companies

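### Does the wider time window in Protocol 5.2.1.2 change the moxifloxacin assay-sensitivity test?

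*Protocol*

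**What the plan says.** Protocol 5.2.1.2, first bullet, gives the endpoint as "The maximum mean difference between moxifloxacin and placebo in QTcF changes from baseline between 20 min to 24 hours after drug administration". SAP Table 6.7.2: 2 lists 11 on-treatment extraction times in that span.

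The synopsis gives the same endpoint as "The maximum mean difference between moxifloxacin and placebo in the QTcF changes from baseline for the time points 2, 3, and 4 hours after dosing". Protocol 7.1.2 has two parts: the changes are analysed at every time from 20 minutes to 24 hours, and the relevant outcome is then the maximum mean difference "in the QTcF changes from baseline for the time points 2, 3, and 4 hours after dosing". It also refers the reader to 5.2.1.2 without noting a difference. SAP 5.2.2 repeats the 7.1.2 text but labels it "CTP Section 5.2.1.2". SAP Section 4 states: "All analyses described in this TSAP are in accordance with the statistical methods described in the CTP".

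For the test, Protocol 7.2 sets the null hypothesis that the moxifloxacin difference "is less than or equal to 5 msec for all of the time points 2, 3, and 4 hours after dosing". Protocol 7.3.2.1 and SAP 7.5.2.1 apply Hochberg to those three hypotheses, with limits of 5%, 2.5% and 1.667%. Both give 90% confidence intervals over the whole profile separately, to describe the time course.

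**The concern.** Two sections of one protocol define a named secondary endpoint over different time sets, and the SAP cites the section that does not contain its text. The maximum over 11 times cannot be smaller than the maximum over three of them, so the reported figure could depend on which section is followed.

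The more serious worry is multiplicity. The Hochberg limits suit three hypotheses. If the wider maximum were compared with 5 msec using those limits, the 5% level would not be protected. If the family were enlarged to 11, the smallest limit would fall to 0.05/11 = 0.4545% and power would drop. Assay sensitivity supports the reading of a negative thorough QT trial, so a loose test here would matter.

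**Working it through.** **1. What each section fixes**

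| Section | Times | What it specifies |
|---|---|---|
| Protocol 5.2.1.2 | 20 min to 24 h | endpoint label only; no hypothesis, threshold or level |
| Synopsis, secondary endpoints | 2, 3, 4 h | endpoint label |
| Protocol 7.1.2, SAP 5.2.2 | all times analysed; outcome at 2, 3, 4 h | endpoint derivation |
| Protocol 7.2 | 2, 3, 4 h | null and alternative hypotheses, 5 msec |
| Protocol 7.3.2.1, SAP 7.5.2.1 | model fitted to all times; test at 2, 3, 4 h | Hochberg, three hypotheses |
| Protocol 7.6 | one of the three times | power at one third of 5% |

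The test is specified in one way throughout. The wide window appears only in a label, in the model fit and in the descriptive profile.

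**2. The plan's power figures**

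Inputs from Protocol 7.6: N = 45, SD of the difference 10 msec, replicate-placebo factor 3/4, level 0.05/3 = 1.667%, effect 12 or 10 msec. The 5 msec threshold is from 7.2.

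- SE = 10 × √(0.75/45) = 1.291 msec.
- Noncentrality = (effect − 5)/SE: 7/1.291 = 5.42 and 5/1.291 = 3.87.
- One-sided noncentral-t power with 44 degrees of freedom (an assumption): 99.9% at 12 msec and 95.0% at 10 msec.

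The protocol prints 99.8% and 93.3%, so both agree within 2 points. A normal approximation at a two-sided 1.667% level gives 93.0% for the second. Either way, these are figures for a family of three.

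**3. Type I error of the planned test**

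In a simulation of 200,000 trials, all true differences were 5 msec, the SE was 1.291 msec, and the times had an assumed first-order autoregressive correlation of 0.3, 0.6 or 0.9. Three-point Hochberg rejects in 4.7%, 4.5% and 3.6% of trials. The 5% level holds.

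**4. The 11-point tests, which no section plans**

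- Under the same null, applying the 1.667% limit to any of 11 times rejects in 15.8%, 13.4% and 7.0% of trials. With independent times it would be 1 − (1 − 0.01667)^11 = 16.9%.
- At 0.4545% per test, single-test power is 99.5% at 12 msec and 86.7% at 10 msec, against 99.9% and 95.0% for three.

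These figures support keeping the family at three, as the plan does.

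**5. The reported maximum**

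The documents give no mean profile or correlation, so both are assumed here. Values are expected maxima in msec at correlation 0.3 / 0.6 / 0.9.

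| Assumed true profile | Maximum over 11 times | Maximum over 2, 3, 4 h | Gap |
|---|---|---|---|
| peak 12 at 2 to 4 h | 13.03 / 12.80 / 12.39 | 12.79 / 12.64 / 12.32 | 0.24 / 0.16 / 0.07 |
| peak 12 at 1 h | 12.36 / 12.19 / 12.01 | 10.36 / 10.24 / 10.04 | 2.00 / 1.95 / 1.97 |

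In the first profile the 11-point maximum falls outside 2, 3 and 4 h in 25 to 30% of trials. In the second, three-point Hochberg still rejects in 96.6 to 99.5% of trials.

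**The case for a change.** The best case for acting needs no multiplicity argument. Protocol 2.2 sends the reader to both Section 5 and Section 7.1.2 for endpoints, no rule says which prevails, and none of the three amendments touches 5.2.1.2. Anyone who follows the SAP's citation lands on a different endpoint. Nor is an early effect excluded by the documents: Protocol 1.2.3 puts moxifloxacin peak concentrations anywhere from 0.5 to 4 hours, and in the early-peak scenario the two maxima differ by about 2 msec.

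The inconsistency and the wrong source reference both stand. They do not leave the analyst in doubt. Protocol 7.1.2 shows how the two time spans fit together: all times enter the analysis and the outcome is read at three. The 5.2.1.2 bullet reads as that text with its last clause lost, and it shares its window with the heart-rate bullets below it. SAP Section 3 says the SAP builds on protocol Section 7, and on moxifloxacin it matches Section 7 exactly. The statement in SAP Section 4 is about statistical methods, so it remains true. The same protocol section, 1.2.3, reports a median time to maximum of 2 hours, which supports the chosen window. The full profile with 90% intervals will be reported in any case, so an earlier peak would be visible.

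**Conclusion.** This is a clerical slip, and no change to the plan follows. One bullet in Protocol 5.2.1.2 carries a wider window than the synopsis, Protocol 7.1.2 and the SAP, and SAP 5.2.2 names the wrong source section.

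The assay-sensitivity test is the same wherever it is defined: three hypotheses at 2, 3 and 4 hours, 5 msec threshold, Hochberg. Its type I error (3.6 to 4.7% in simulation), its power, the 45 subjects and the decision rule do not depend on the bullet. The inflated error rates and the lost power belong to 11-point tests that nobody planned.

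The only quantity that could differ is the reported maximum, by 0.07 to 0.24 msec for a peak at 2 to 4 hours and by about 2 msec for a peak at 1 hour. The SAP already fixes it as the maximum over 2, 3 and 4 hours. The sizes rest on the protocol's SD of 10 msec and on assumed profiles and correlations. The conclusion about the test rests on the text alone.
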